4.1 Enrollment/screening period

Procedures will be performed according to the Study Plan, Table 6.

During screening, consenting subjects are assessed to ensure that they meet study eligibility criteria per Section 3. Subjects who do not meet these criteria must not be enrolled in the study.

Subjects will be considered enrolled once the subject has signed the Informed Consent Form (full study) and has met all inclusion and none of the exclusion criteria. Note: Prior to any cohort being filled, subjects can initiate study drug treatment prior to cohort assignment. Once a cohort has been closed to further enrollment, subjects may not initiate treatment until the Myriad BRACAnalysis CDx[®] and myChoice[®] HRD testing demonstrates the subject is eligible for an open cohort, at which point the subject may initiate study drug. If the results demonstrate the subject was eligible for a closed cohort, the subject will be discontinued from the study. See Section 3.5 for information about cohort assignment.

The following procedures can be performed at pre-screening if the subject has consented to pre-screening:

- Obtain informed consent specifically for central Myriad HRD tumor (myChoice[®] HRD) and gBRCA testing (BRACAnalysis CDx[®]);
- Obtain blood sample for determination/confirmation of BRCA status via Myriad BRACAnalysis CDx[®] (see Table 8); and
- Obtain archival tumor sample and/or baseline tumor sample for Myriad testing; subjects must provide a tumor sample to be considered for the study the sample can either be an archival sample or a new baseline tumor sample (see Section 5.6);

The following procedures will be performed at screening (Day -28 to Day -1):

- Obtain informed consent specifically for central Myriad HRD tumor (myChoice[®] HRD) and gBRCA testing (BRACAnalysis CDx[®]) if not previously obtained through pre-screening consent;
- Obtain informed consent for overall study; and
- Confirm eligibility based on all inclusion/exclusion criteria (see Sections 3.1 and 3.2);
- Obtain demographics and medical and surgical history;
- Obtain prior cancer therapies, including radiotherapy;

- Obtain blood sample for determination/confirmation of BRCA status via Myriad BRACAnalysis CDx[®] (see Table 8) if not previously obtained for Myriad testing;
- Obtain archival tumor sample and/or baseline tumor sample(s); subjects must provide a tumor sample to be considered for the study the sample can either be an archival sample or a new baseline tumor sample (see Section 5.6); Note: The tumor sample for Myriad HRD testing should only be taken if not previously obtained through pre-screening. CCI
- Assess functional status using the ECOG performance status scale (see Appendix F);
- Perform physical examination (see Section 5.2.2);
- Obtain vital signs, body weight, and body height (see Section 5.2.4);
- Obtain ECG (see Section 5.2.3);
- Obtain sample for hematology and clinical chemistry (see Section 5.2.1 and Table 8);
- Obtain sample for urinalysis (see Section 5.2.1 and Table 7);
- Obtain sample for pregnancy test, if necessary (see Section 5.2.5.1);
- Assess tumor (CT or MRI according to RECIST v1.1) (see Section 5.1.1);
- Assess and record concomitant medications (including blood transfusions); and
- Assess subject for adverse events (continuous from time of informed consent).

4.2 Treatment period

Descriptions of the procedures for this period are included in the Study Plan, Table 6.

4.2.1 Study Visit 2, Day 1

The following procedures will be performed at Visit 2, Day 1:

- Obtain sample for pregnancy test, if necessary (see Section 5.2.5.1);
- Enroll subject;

- Perform physical examination (see Section 5.2.2);
- Obtain vital signs, body weight, and ECG (see Sections 5.2.3 and 5.2.4);
- Assess functional status using the ECOG performance status scale (see Appendix F);
- Obtain pre-dose blood sample for hematology/clinical chemistry (see Section 5.2.1 and Table 8);
- Obtain pre-dose blood sample for disease specific marker (CA-125) (see Section 5.2.1.4 and Table 8);
- Obtain pre-dose blood sample for PGx (see Section 5.6 and Table 8);

•	CCI	
•	CCI	
	CCI	

- Dispense olaparib;
- Assess and record concomitant medications including history of blood transfusions (within the previous 120 days from informed consent and the reasons); and
- Assess subject for adverse events (continuous from time of informed consent).

4.2.2 Study Visit 3, Day 8 to Visit 5, Day 22

The following procedures will be performed at Visit 3, Day 8; Visit 4, Day 15; and Visit 5, Day 22 (\pm 3 days):

- Obtain blood sample for hematology/clinical chemistry (see Section 5.2.1 and Table 8);
- Assess and record concomitant medications including blood transfusions; and
- Assess subject for adverse events (continuous from time of informed consent).

4.2.3 Study Visit 6, Day 29

The following procedures will be performed at Visit 6, Day 29 (\pm 3 days):

- Obtain blood sample for hematology/clinical chemistry (see Section 5.2.1 and Table 8);
- Obtain blood sample for disease specific marker (CA-125) (see Section 5.2.1.4 and Table 8);
- Assess and record concomitant medications including blood transfusions;
- Assess subject for adverse events (continuous from time of informed consent); and
- Dispense/return olaparib.

4.2.4 Study Visit 7, Day 57, and every 4 weeks onwards

Subsequent on-treatment visits for the active treatment period will take place on Day 1 of a 4-week visit period up to 52 weeks (if not progressed and still on treatment), then on Day 1 of a 12-week visit period relative to date of enrollment until PD (RECIST v1.1). Subsequent on-treatment visits for subjects who remain on treatment post-progression should take place every 12 weeks. Tumor assessment visits will be performed at the end of every 8 weeks (± 1 week) up to 48 weeks, then every 12 weeks (± 1 week) relative to date of enrollment until PD (RECIST v1.1). Subjects will be contacted to assess for survival every 12 weeks following disease progression until death, withdrawal of consent, or study closure. See Section 4.4.

The following procedures will be performed at Visit 7, Day 57 (\pm 3 days) and every 4 weeks onward (i.e., Visit 8 [Day 85], Visit 9 [Day 113], etc.) through the active treatment period:

- Assess functional status using the ECOG performance status scale (see Appendix F);
- Obtain blood sample for hematology/clinical chemistry (see Section 5.2.1 and Table 8);
- Obtain blood sample for disease specific marker (CA-125) (see Section 5.2.1.4 and Table 8);
- Assess tumor (CT or MRI according to RECIST v1.1) (see Section 5.1.1);
- Note: The tumor assessments according to RECIST v1.1 will be performed every 8 weeks (± 1 week) from the first dose of study drug (Visit 2) for 48 weeks, and then every 12 weeks (± 1 week) (relative to the date of enrollment) thereafter until determined by the Investigator according to RECIST v1.1 criteria (including confirmatory RECIST scan).
- Assess and record concomitant medications including blood transfusions;
- Assess subject for adverse events (continuous from time of informed consent); and
- Dispense/return olaparib.

4.2.5 Study Treatment Discontinuation Visit

Subjects should be discontinued from study treatment if they have objective radiological disease progression according to RECIST v1.1 (see Appendix G) and complete the Study Treatment Discontinuation Visit as per the study plan.

The following procedures will be performed at the Study Treatment Discontinuation Visit (+ 7 days):

- Perform physical examination (see Section 5.2.2);
- Assess functional status using the ECOG performance status scale (see Appendix F);
- Obtain blood sample for hematology/clinical chemistry (see Section 5.2.1 and Table 8);
- Obtain blood sample for disease specific marker (CA-125) (see Section 5.2.1.4 and Table 8);

•	CCI
•	CCI
٠	CCI

- Assess and record concomitant medications including blood transfusions;
- Assess subject for adverse events (continuous from time of informed consent); and
- Return olaparib.

4.3 Follow-up period

4.3.1 Follow-up 30 days after the last dose of olaparib (Follow-up Visit)

A Follow-up Visit should be conducted 30 days (\pm 7 days) after the last dose of olaparib. Any SAEs or adverse events ongoing at the time of the Study Treatment Discontinuation Visit or which have occurred during the defined 30-day follow-up period must be followed-up (in accordance with Section 6.3.1). Appropriate safety evaluations should be repeated and/or additional tests performed at any time when clinically indicated, or at the discretion of the Investigator, until resolution, unless, in the Investigator's opinion, the condition is unlikely to resolve due to the subject's underlying disease. If the subject is lost to follow-up, then this should be noted in the eCRF.

The following assessments will be performed:

- Obtain vital signs, body weight, and ECG (see Sections 5.2.3 and 5.2.4);
- Obtain sample for pregnancy test, if necessary (see Section 5.2.5.1);
- Obtain blood sample for hematology/clinical chemistry (see Section 5.2.1 and Table 8);
- Assess and record concomitant medications including blood transfusions;
- Assess subject for adverse events (continuous from time of informed consent) (see Section 6.3.1); and
- Record subsequent cancer therapy following discontinuation of study treatment.

During the follow-up period, subjects will be followed for PFS (CA-125 and radiographic evidence of progression per site standards) until database lock/end of study and assessed for OS.

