3.9.1 Procedures for discontinuation of a subject from investigational product

At any time, subjects are free to discontinue olaparib or withdraw from the active treatment phase of the study (i.e., olaparib and assessments – see Section 3.10), without prejudice to further treatment. A subject who decides to discontinue olaparib will complete the Study Treatment Discontinuation Visit (see Section 4.2.5) and will be asked about the reason(s) for discontinuation and the presence of any adverse events. Adverse events will be followed-up (see Section 6), and all study medications should be returned by the subject.

By discontinuing from study treatment, the subject then enters the survival follow-up phase of the study. Subjects should be followed for progression (if discontinuation in the absence of progression) and survival following treatment discontinuation as per the study plan (see Section 4.3 and Table 6). Any subject who has not yet shown objective radiological disease progression at withdrawal from olaparib should continue to be followed as per RECIST v1.1.

Any subject discontinuing olaparib should be seen at 30 days post-discontinuation for the evaluations outlined in the study plan. The subject's tumor status should be assessed clinically, and, if appropriate, disease progression should be confirmed by radiological assessment via RECIST v1.1 criteria. After discontinuation of study medication, the Principal Investigator/Sub-Investigator will perform the best possible observation(s), test(s), and evaluation(s), as well as give appropriate medication and all possible measures for the safety of the subject. In addition, they will record in the electronic case report form (eCRF) the date of discontinuation, the reasons, manifestation, and treatment at the time of discontinuation. If a subject discontinues study treatment, the AstraZeneca Representative Study Physician must be informed immediately. The Subject will be required to attend the treatment discontinuation visit.

After discontinuation of the study medication at any point in the study, all ongoing adverse events or SAEs must be followed until resolution unless, in the Investigator's opinion, the condition is unlikely to resolve due to the subject's underlying disease, or the subject is lost to

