follow-up (see Section 6.3.2). All new adverse events and SAEs occurring during the 30 calendar days after the last dose of study medication must be reported (if SAEs, they must be reported to AstraZeneca Safety representative **within 24 hours** as described in Section 6.4) and followed to resolution as above. Subjects should be seen at least 30 days after discontinuing study medication to collect and/or complete adverse event information. For guidance on reporting adverse events after the 30 day follow-up period see Section 6.3.1.1.

All subjects who received at least 1 dose of olaparib must be followed for progression and survival through the final analysis of all primary and secondary endpoints (approximately 6 months after the last subject has commenced study treatment [received at least 1 dose of olaparib]) + an additional 12 months after the data cut-off for follow-up for survival for applicable subjects. At the end of this additional 12 months of survival follow-up, updated OS and safety analyses will be conducted and the study will be closed. Subjects are, however, permitted to continue to receive olaparib beyond the closure of the database if, in the opinion of the Investigator, they are continuing to receive benefit from treatment with olaparib. During this time, adverse events of special interest and SAEs must still be collected and reported until 30 days after the subject finally stops taking olaparib. See Section 4.3.

If a subject is withdrawn from the study, see Section 3.10. See Section 3.10.2 for details on subject replacement.

For information regarding the withdrawal of consent for donated biological samples, see Section 5.6.9.

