- q. When an adverse event for nausea and vomiting occurs, an additional eCRF will require completion. All ongoing adverse events/SAEs and any new adverse events/SAEs identified during the 30 calendar day follow-up period after last dose of study medication must be followed to resolution (or stabilization or return to baseline). A targeted questionnaire will be sent to any Investigator reporting an AESI as an aid to provide further detailed information on the event.
- Sufficient olaparib should be dispensed for at least each active treatment period plus overage; however, additional treatment can be dispensed to subjects to last longer in accordance with local practice.
- s. All anti-cancer treatments (including, but not limited to, chemotherapy and targeted agents), and the Investigator's opinion of response to them plus the date of progression, post-discontinuation of study treatment, need to be recorded.
- t. Only 1 sample should be collected per subject for pharmacogenetics during the study. The sample should be taken pre-dose.
- u. Subjects must provide a tumor sample to be considered for the study the sample can either be an archival sample or a new baseline tumor sample. If a tumor sample is taken at pre-screening for Myriad testing a sample will not need to be re-taken for Myriad testing; independent of the tumor sample for Myriad testing, an additional sample must be provided at screening for future research purposes.
- v. The biopsied tumor should not be assessed as a target lesion as part of the RECIST assessments if there are other lesions available. The biopsy should be taken after the baseline scan has been performed.

CCI		

AESI = adverse event of special interest; BP = blood pressure; CA = Cancer antigen; CT = computed tomography; CC

ECG = electrocardiogram; ECOG = Eastern Cooperative Oncology Group; eCRF = electronic case report form; gBRCA = germline BRCA; GCIG = Gynecological Cancer Intergroup; HRD = homologous recombination deficiency; MRI = magnetic resonance imaging; No. = number; PD = progressive disease; PFS = progression-free survival; RECIST = Response Evaluation Criteria in Solid Tumors; SAE = serious adverse event.

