4.4 Survival follow-up

All subjects who enrolled and received at least 1 dose of olaparib will be followed for survival. Subjects will be contacted to assess for survival status every 12 weeks following disease progression until death, withdrawal of consent, or study closure. Survival information may be obtained via telephone or email contact with the subject, subject's family, or by contact with the subject's current physician. The vital status of the subject can be obtained by site personnel from publicly available resources where it is possible to do so under applicable local laws.

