6.3.1.1 Adverse events after the 30 day follow-up period

For pharmacovigilance purposes and characterization, any case of MDS/AML or new primary malignancy occurring after the 30 day follow-up period should be reported to the AstraZeneca Safety Representative whether it is considered a non-serious adverse event (e.g., non-melanoma skin cancer) or an SAE, and regardless of the Investigator's assessment of causality. Investigators will be asked during the regular follow-up for survival if the subject has developed MDS/AML or a new primary malignancy, and will be prompted to report any such cases.

At any time after a subject has completed the study (i.e., no longer receiving study drug and past the 30 day follow-up period), if an Investigator learns of any SAE, including sudden death of unknown cause, and he/she considers there is a reasonable possibility that the event is causally related to olaparib, the Investigator should notify the AstraZeneca Safety Representative.

Otherwise, after study treatment completion (i.e., after any scheduled post-treatment follow-up period has ended), there is no obligation to actively report information on new adverse events or SAEs occurring in former study subjects.

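### The ± 7 day window on the 30-day Follow-up Visit lets the last scheduled adverse-event enquiry fall up to 7 days before the 30-day reporting period ends, in conflict with Section 3.9.1

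*Protocol*

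**What the plan says.** Three places in the Protocol set the timing of the last general adverse-event visit, and they do not agree.

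- Section 4.3.1: "A Follow-up Visit should be conducted 30 days (\pm 7 days) after the last dose of olaparib". The visit-window row of Table 6 shows the same ± 7 days for this column.
- Section 3.9.1, on the evaluations: "Any subject discontinuing olaparib should be seen at 30 days post-discontinuation for the evaluations outlined in the study plan". No window is given.
- Section 3.9.1, on adverse events: "Subjects should be seen at least 30 days after discontinuing study medication to collect and/or complete adverse event information".

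The reporting period itself is stated consistently. Section 3.9.1 says "All new adverse events and SAEs occurring during the 30 calendar days after the last dose of study medication must be reported", and footnote q of Table 6 says that "any new adverse events/SAEs identified during the 30 calendar day follow-up period after last dose of study medication must be followed to resolution".

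After this visit the scheduled enquiry narrows. The adverse-event row of Table 6 is marked up to and including the 30-day Follow-up Visit and not under Overall Survival Follow-up. Section 4.4 provides that "Subjects will be contacted to assess for survival status every 12 weeks following disease progression until death, withdrawal of consent, or study closure". Section 6.3.1.1 describes what is asked then: "Investigators will be asked during the regular follow-up for survival if the subject has developed MDS/AML or a new primary malignancy".

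**The concern.** The visit exists to close adverse-event collection for a period that runs to day 30. If it is held before day 30, part of that period is still to come, and the schedule has no later point at which a general question about health problems is put to the subject. Section 6.3.5 lists three sources of adverse events: spontaneous reports, observation, and an open question about problems since the subject was last asked. After an early visit the open question is not scheduled again.

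Safety and tolerability in each cohort is a stated objective (Section 2.3) and is summarised descriptively. The completeness of the last days of the window would then depend on when a subject happened to be booked. A site also cannot tell from the text whether a visit on day 25, say, is compliant.

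**Working it through.** The Protocol states no figure for this gap, so there is none to reproduce. The check is day arithmetic followed by a search for any later contact that would close the gap.

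**Inputs**
- Target day 30 after the last dose, tolerance ± 7 days (Section 4.3.1, Table 6).
- Reporting period: 30 calendar days after the last dose (Section 3.9.1, Table 6 footnote q).
- Earliest visit day under the adverse-event sentence of Section 3.9.1: day 30.
- Assumption: discontinuation and last dose are counted from the same day. Section 3.9.1 uses the first term for the visit, and Section 4.3.1 uses the second.

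**Permitted days**
- Earliest: 30 − 7 = 23. Latest: 30 + 7 = 37.
- Days 30 to 37 satisfy both Section 4.3.1 and the at-least-30-days sentence.
- Days 23 to 29 satisfy Section 4.3.1 and Table 6 only.

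**Days without a scheduled enquiry**, for a visit on day v: gap = max(0, 30 − v)

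| Visit day v | Gap (days) | Share of 30 days |
|---|---|---|
| 23 | 7 (days 24 to 30) | 7/30 = 23% |
| 26 | 4 | 4/30 = 13% |
| 29 | 1 | 1/30 = 3% |
| 30 to 37 | 0 | 0% |

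**Does a later contact close the gap?**
- Survival contacts (Sections 4.4 and 6.3.1.1): these come every 12 weeks after progression and prompt only for MDS/AML and new primary malignancy.
- Adverse-event assessment in Section 4.3.2: this applies after the primary data cut-off and refers back to Section 6.3.1.1, so it is not a general enquiry about days 24 to 30.
- Tumour assessments in subjects who stop before progression (Sections 3.9.1 and 5.1.1): scans continue, but Table 6 attaches no adverse-event enquiry to them after the 30-day visit.
- Follow-up of events still ongoing at the 30-day visit (Section 6.3.2): this concerns known events. A new one might come to light in passing, but nothing schedules the question.

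None of these closes the gap by design. If the last enquiry cannot fall before day 30, the maximum gap goes from 7 days to 0.

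**The case against.** The best defence is that an early visit removes a prompt and not an obligation. The duty to report through day 30 stands in Section 3.9.1 whatever the visit date, and Section 6.3.1 has collection running continuously through follow-up. Section 6.3.1.1 does say "there is no obligation to actively report information on new adverse events or SAEs occurring in former study subjects", but only once scheduled post-treatment follow-up has ended, so it does not release sites from days 24 to 30. The window also permits an early visit without forcing one, and both timing sentences say should. All of this stands. The right description is that the Study Plan does not guarantee coverage of the 30 days. A reader might infer that it cannot deliver the window, or that events in the gap go unreported, and the text supports neither.

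Three further inferences are tempting and also fail.
- **Deaths.** Section 6.3.11 requires all deaths within the 30-day period to be reported, and Sections 4.4 and 8.4.3.6 follow vital status in treated subjects through contacts, physicians or public records. A death on day 27 does not depend on the clinic visit to be found.
- **Laboratory toxicity.** The visit takes one blood sample. That is one time point whether it is drawn on day 23, 30 or 37.
- **Pregnancy testing.** Section 5.2.5.1 ties the test to the 30-day visit, and nothing says that it must follow the end of the one-month period. Section 6.6.1 separately tracks conceptions to 1 month after the last dose. There is no contradiction here.

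The study is also non-comparative and descriptive, so variation in visit timing cannot bias a treatment contrast. The late risks singled out in the Protocol, MDS/AML and new primary malignancy, are actively asked about after day 30. These points limit the importance of the conflict but do not reconcile the passages.

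**Conclusion.** The inconsistency is real and minor. A visit on days 23 to 29 complies with Section 4.3.1 and Table 6, departs from the at-least-30-days sentence of Section 3.9.1, and leaves 1 to 7 of 30 days without a scheduled adverse-event enquiry. The 23% is the worst case for a single subject.

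No average across subjects can be given, because the Protocol does not say how visits will be spread within the window. The average could be anything from 0 days (all visits on day 30 or later) to 7 days (all on day 23), and a target of day 30 makes the upper end unlikely.

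What is realistically at risk is new, mainly non-serious events that start in those days and are not volunteered. Serious events that reach the site must still be reported within 24 hours of awareness (Section 6.4). The primary ORR analysis is not touched.

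**What to change.** Reconcile Sections 3.9.1 and 4.3.1 and Table 6 so that the last adverse-event enquiry cannot fall before day 30 after the last dose. Either of two edits is enough:

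1. In Section 4.3.1 and the Table 6 window row, change the Follow-up Visit window from ± 7 days to 0 to + 7 days (days 30 to 37), and give the same window in both sentences of Section 3.9.1. Table 6 already uses a one-sided window for the treatment discontinuation visit, so the format is familiar to sites, though this does not show that the present ± 7 days was a slip.
2. Keep ± 7 days, but require a phone contact on or after day 30 for any subject seen earlier, to complete adverse-event collection, and add it to Table 6.

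The first adds no visit and costs a little scheduling flexibility. The second keeps the flexibility and costs a short call for subjects seen on days 23 to 29.
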